## Background to Research Questions

- Iron is an important component of hemoglobin, and an essential part of erythropoiesis. It is also a necessary micronutrient for rapidly proliferating and differentiating cells and tissues especially in the brain. Iron deficiency in infancy has been associated with anemia and impaired neurodevelopmental outcomes that extend into childhood. Premature infants are at highest risk for iron deficiency because they are deprived of the iron accretion that occurs in the third trimester of pregnancy, are born with lower iron stores compared to their term counterparts, and have increased utilization and depletion of iron stores with their rapid growth rate.

- While there is no biomarker that serves as a gold standard for iron status in premature infants, hemoglobin (Hgb) levels and mean corpuscular volume (MCV) have been previously used, though they are late markers of iron deficiency. Ferritin, an acute phase reactant, has also been used as biochemical marker of iron deficiency, but is often abnormally elevated during inflammatory states. Obtaining a combination of ferritin and a complete blood count for Hgb and MCV levels to characterize iron stores requires additional blood volume and predisposes the neonate to iatrogenic blood loss from frequent phlebotomy. Iron-limited erythropoiesis can be better recognized by Ret-Hb even in preterm neonates <29 weeks' gestation, and can result from the same sample obtained to evaluate Hgb and MCV. Ret-Hb levels >29 pg have been considered as iron-replete.
- In older populations, EOD iron supplementation is as effective as daily iron supplementation in the treatment of iron deficiency anemia, with studies revealing significantly fewer gastrointestinal side effects in those who are on EOD iron. Adults regulate their iron status through a feedback pathway involving hepcidin whereby iron-sufficient individuals will have upregulated hepcidin, which leads to decreased iron absorption and availability. Recent studies have revealed that pediatric patients and premature neonates regulate iron absorption through hepcidin in a similar fashion. A randomized control trial in Kenya found that consecutive day iron dosing increases hepcidin and decreases iron absorption, compared with EOD dosing in pediatric patients as young as 5 months of age. Though the regulation of iron status through hepcidin has been studied in extremely premature neonates, the clinical effect of EOD dosing of iron has not yet been examined in this population.

## METHODOLOGY

### Study design

- This is a non-inferiority, blinded, randomized control trial designed to investigate if EOD iron is comparable to daily iron dosing in achieving iron replete status by Ret-Hb measurements in premature infants.

### Intervention

- The control group / current standard for iron supplementation in neonates is detailed as follows: after the infant achieves full enteral feeds, the infant is started on 6 mg/kg of oral iron daily supplementation. Though the American Academy of Pediatrics and World Health Recommendation recommend 2 – 4 mg/kg of supplemental iron for premature infants, studies examining the effects of higher dose of enteral iron supplementation (3.4 mg/kg to 7.1 mg/kg per day) revealed no differences between the lower versus higher dosages on morbidity (sepsis, necrotizing enterocolitis, or enteral feeding intolerance) and mortality outcomes. The dose of 6 mg/kg of enteral iron was chosen based on the aforementioned recommendations with evidence of its safety, while minimizing the need to increase the enteral iron dosage if an infant were to be started on ESAs where a dose of 6 mg/kg of enteral iron supplementation is the standard practice. Phlebotomy to obtain a complete blood count, reticulocyte count, and reticulocyte hemoglobin count is pursued the Monday after iron supplementation is started and every 2 weeks thereafter to monitor hematocrit or hemoglobin levels and iron status.

- The intervention group for EOD iron supplementation in neonates is as follows: after the infant achieves full enteral feeds, the infant is started on 6mg/kg of oral iron supplementation administered every other day. Phlebotomy to obtain a complete blood count, reticulocyte count, and reticulocyte hemoglobin count is pursued the Monday after starting iron supplementation and every 2 weeks thereafter to monitor hematocrit or hemoglobin levels and iron status. There is literature revealing that neonates even <29 weeks' gestation absorb and regulate iron similar to adults. There is literature revealing that there is no difference between EOD and daily iron supplementation in older pediatric populations and adults in improving hemoglobin levels, with one study in Switzerland revealing that EOD iron reduced iron deficiency in the longer term and triggered fewer gastrointestinal side effects in adult women. Given the evidence that premature infants regulate their iron status similarly to older infants and adults, and the current evidence of EOD iron in older children and adults, this intervention, compared with our control, will help us address our primary question to determine if EOD iron is non-inferior to daily iron.
- Phlebotomy to obtain a complete blood count, reticulocyte count, and reticulocyte hemoglobin count may be pursued sooner than the 2-week mark based on physician judgment and the clinical status of the infant.
- Parents or guardians of infants who meet inclusion criteria will be consented prior to enrollment into the study. Following written informed consent, eligible participants will be randomized by simple randomization to the EOD arm or daily arm by computer generated sequence of random numbers. Allocation will be concealed using sequentially numbered opaque sealed envelopes which will be unknown to the investigators. The random sequence will be generated by a statistician who will not be directly involved in the care of patients.
- All study-related materials will be destroyed after official closure has been confirmed by the IRB.

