### **Setting**

- The study will be conducted in the neonatal intensive care unit at two sites: CHRISTUS Children's and Brooke Army Medical Center.

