### **Study Subjects**

- The population to be studied include premature infants who completed 26 0/7 to 32 6/7 weeks' gestation. We will include premature infants who are on full enteral feeds and are started on oral iron

therapy. Infants with known congenital anomalies or chromosomal abnormalities (such as Trisomy 18 or Trisomy 21), conditions that affect iron metabolism (such as thalassemia or hemochromatosis), bleeding disorders or coagulopathy, and received iron parenterally will be excluded from the study.

- There will be need for a written consent from the patient's' parent or legal guardian. A copy of the written consent will be included in the appendix.
- Our target population are neonates, which fall under the category of special subject population. Literature on the benefits of every other day iron dosing compared with daily iron dosing is already available in older pediatric patients and adults. There have been no studies investigating their benefits in the neonatal population, despite this population being the most vulnerable to iron deficiency and its consequences, as well as emerging evidence that neonate regular iron metabolism similar to adults.

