## Data Analysis

- A sample size determination was conducted using Riskcalc.org (Chow S-C, Shao J, Wang H, Lokhnygina Y. Sample Size Calculations in Clinical Research. Third ed: Chapman and Hall/CRC; 2017.) and confirmed by [name] (BAMC Statistician). Sample size estimates are for type 1 error of 5% ( $\alpha = 0.05$ ), power ( $1-\beta$ ) of 80%, ratio of 1:1 of intervention to control. The effect size is determined by estimating the proportion of infants with Ret-Hgb >29 pg to be similar at 80% between daily versus EOD iron, with a margin of 20%. It was determined that a sample size of 100 patients would be needed for this study (50 for intervention, and 50 for control).
- A statistician who is blinded to the study allocation will analyze the data. All statistical analyses will be performed with IBM SPSS Statistics (Armonk, NY: IBM Corp) and JASP Team (2022). JASP, Version 0.16.1 (Netherlands: JASP Team). Descriptive statistics will be performed for all variables. Categorical data will be reported as percentages, and continuous data will be reported as medians with interquartile range or means with standard deviation. The two groups will be compared according to the intention to treat with the use of Student's t-tests, Mann-Whitney-U tests, chi-square analysis based on the outcome being evaluated. All p-values will be one-sided, with a statistical significance level of <0.05. Covariates to include gestational age, in-born versus out-born infants, ESA use, receipt of pRBC transfusion will be controlled for using a logistic regression model and will be reported with an odds ratio (OR) and 95% confidence intervals (CI). A medical monitor who is not involved in the study will be assigned prior to the initial enrollment of the trial to monitor the data periodically (every 3 months) to ensure the safety of the participants and the scientific integrity of the study. An interim analysis will be performed at halfway to target enrollment.

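### Simple randomisation of 100 infants at two hospitals leaves site and gestational age unbalanced by design; stratified blocks would be a cheap, minor improvement

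*Protocol*

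**What the plan says.** The Intervention section fixes the method: "eligible participants will be randomized by simple randomization to the EOD arm or daily arm", from a computer-generated random list. It continues: "Allocation will be concealed using sequentially numbered opaque sealed envelopes which will be unknown to the investigators". A statistician outside the infants' care generates the sequence. Blocks and strata are not mentioned, and the section does not say how the envelope series is to run across hospitals.

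The Setting section says: "The study will be conducted in the neonatal intensive care unit at two sites". The Study Subjects section defines the population as "premature infants who completed 26 0/7 to 32 6/7 weeks' gestation", and the primary objective is assessed at 36 weeks post-menstrual age.

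The Data Analysis section plans 50 infants per arm, with a "ratio of 1:1 of intervention to control". It lists chi-square among the group comparisons and adds a logistic regression: "Covariates to include gestational age, in-born versus out-born infants", followed by ESA use and pRBC transfusion. Site is not in that list. The adjusted result is to be reported as an odds ratio.

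**The concern.** The protocol itself makes this choice, so it is not a detail left to an analysis plan that is not shown.

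Gestational age matters for this endpoint by the protocol's own account. The Background links prematurity to missed third-trimester iron accretion and lower stores, and Data Analysis lists gestational age as a covariate. Because the endpoint is read at a fixed post-menstrual age, an infant born at 26 0/7 weeks has 10 weeks from birth to 36 0/7, while one born at 32 6/7 has 3 1/7 weeks. Iron exposure is shorter still, since it starts only at full enteral feeds.

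Site is neither balanced nor adjusted for. In-born versus out-born status, which is a listed covariate, is a different variable.

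With about 50 infants per arm, a visible chance imbalance in either factor is quite possible. In a non-inferiority trial with a 20-point margin, it would invite the question of whether similar proportions reflect similar treatments or different infants. The chi-square comparison has no answer to that. The logistic model has a partial one, but on the odds-ratio scale, whereas the margin is in percentage points.

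**Working it through.** **Inputs from the protocol (Data Analysis, Study Subjects, Setting).** 80% replete in both arms; margin 20 points; one-sided alpha 0.05; power 80%; 50 + 50 infants; gestational age 26 0/7 to 32 6/7 weeks; two sites.

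**Assumptions, because the protocol gives no mix.** Gestational age uniform over the seven-week range; one site enrolling 20 to 30 infants.

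**1. Reproduce the sample size.** n per arm = (1.645 + 0.842)² × (0.16 + 0.16) / 0.20² = 49.5, so 50 per arm and 100 in total. This matches the plan.

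**2. Does power depend on the split?** Power = Φ(0.20 / √(0.16/n₁ + 0.16/n₂) − 1.645). Probabilities are from Binomial(100, 0.5).

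| Split | Power | Probability of this split or worse |
|---|---|---|
| 50/50 | 80.4% | (exactly 50/50: 8.0%) |
| 45/55 | 80.0% | 36.8% |
| 40/60 | 78.9% | 5.7% |
| 35/65 | 77.0% | 0.35% |

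Averaged over all splits, power is 80.0%. Blocking gains about 0.4 points.

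**3. The half-way look (about 50 infants).** A 20/30 split or worse has probability 20.3%. At 20/30, though, the standard error grows only by the factor √(1/30 + 1/20) / √(2/25) = 0.289 / 0.283 = 1.02.

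**4. Balance in gestational age (50 per arm, normal approximation).**
- Mean: SD of one infant = 7/√12 = 2.02 weeks. SD of the arm difference = 2.02 × √(2/50) = 0.404 week. P(difference above 0.5 week) = 2 × [1 − Φ(0.5/0.404)] = 0.216.
- Share under 30 weeks: p = 4/7 = 0.571. SD of the difference = √(0.571 × 0.429 × 2/50) = 0.099. P(15 points or more) = 2 × [1 − Φ(0.15/0.099)] = 0.130.

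**5. Balance in any binary factor, including site.** If 30% to 50% of infants have the factor (assumed), the arms differ by 10 points or more with probability 28% to 32%, and by 20 points or more with probability 3% to 5%.

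**6. Split within the smaller site.** With 20 infants, P(6/14 or worse) = 11.5%. With 30 infants, P(10/20 or worse) = 9.9%. Between those sizes, the chance of 2:1 or worse moves between 6.1% (29 infants) and 18.9% (21 infants), because only whole-number splits are possible.

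**7. Scale of the effect on the endpoint (illustration, assumed).** If infants under 30 weeks were replete 20 points less often, a 15-point imbalance would move the arm difference by 0.20 × 0.15 = 3 points. The standard error of the difference at 50/50 is √(2 × 0.16/50) = 8 points.

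**The case against.** A reader might infer that the power calculation fails because simple randomisation will rarely give exactly 50 and 50. The documents do not support that. The 1:1 ratio is the expected allocation, which simple randomisation meets, and power is flat across any likely split (step 2). The half-way look gives no stronger case: an uneven split there costs about 2% in standard error.

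Nor does chance imbalance bias the estimate or inflate the type I error over repeated trials. It is part of the sampling variation that the unadjusted test and interval already reflect.

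Gestational age is also in the planned logistic model, so it would be wrong to say that the analysis ignores it. Nothing in the protocol shows that site predicts the outcome: both hospitals follow one protocol and use the same analyser (Equipment/Supplies/Services). The balance figures rest on assumed mixes, and the illustrated shift of 3 points is small beside a 20-point margin.

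Finally, unrestricted randomisation is the least predictable method. The protocol says "This is a non-inferiority, blinded, randomized control trial" but describes no placebo. If staff can tell the two schedules apart, blocks within small strata become partly predictable.

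All of this stands, and it limits the point to a minor one. It does not remove it. Gestational age is prognostic by the protocol's own account, the chi-square comparison does not use it, and site is covered by neither design nor analysis. The predictability cost is real but can be limited by block sizes that vary and stay concealed.

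**Conclusion.** The point holds as a minor matter of precision and credibility. Simple randomisation is valid here, and the stated sample size reproduces exactly; the protocol says nothing false on this point. What it leaves open is a moderate chance of visible imbalance: about 22% for a mean gestational-age difference above 0.5 week, about 13% for a gap of 15 points or more in the share under 30 weeks, and roughly 10% to 12% for a 2:1 or worse split at a site of 20 or 30 infants. These figures depend on the assumed uniform gestational age and assumed site sizes. The gap is clearest for site, which is neither stratified nor adjusted for. For gestational age the planned logistic model already gives partial protection.

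**What to change.** Before enrolment starts:

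- Have the statistician generate the list in permuted blocks of randomly varying, concealed size, stratified by site and by gestational age (for example below 30 0/7 weeks against 30 0/7 and above).
- Prepare a separate sealed-envelope series for each of the four strata. This also settles how numbering runs across the two hospitals.
- Add site to the covariates in Data Analysis; gestational age is already there.

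The cost is a new list and four envelope series in place of a single one, plus slight predictability at block ends if staff can tell the schedules apart. Random, concealed block sizes limit that. The sample size need not change. Stratification is easy to introduce before enrolment, while an imbalance in the realised groups cannot be undone afterwards.

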### **Setting**

- The study will be conducted in the neonatal intensive care unit at two sites: CHRISTUS Children's and Brooke Army Medical Center.

### **Expected Start Date**

- Upon IRB approval

### **Duration of Study**

- We anticipate the duration of the study begin upon IRB approval date and patient accrual will continue for until we have our target number of patients that meet inclusion criteria based on sample size analysis. We estimate this to be achievable within a 12-24-month period. Data analysis is anticipated to be completed within three months from the date of final patient accrual.

### **Study Subjects**

- The population to be studied include premature infants who completed 26 0/7 to 32 6/7 weeks' gestation. We will include premature infants who are on full enteral feeds and are started on oral iron

therapy. Infants with known congenital anomalies or chromosomal abnormalities (such as Trisomy 18 or Trisomy 21), conditions that affect iron metabolism (such as thalassemia or hemochromatosis), bleeding disorders or coagulopathy, and received iron parenterally will be excluded from the study.

- There will be need for a written consent from the patient's' parent or legal guardian. A copy of the written consent will be included in the appendix.
- Our target population are neonates, which fall under the category of special subject population. Literature on the benefits of every other day iron dosing compared with daily iron dosing is already available in older pediatric patients and adults. There have been no studies investigating their benefits in the neonatal population, despite this population being the most vulnerable to iron deficiency and its consequences, as well as emerging evidence that neonate regular iron metabolism similar to adults.

### **Equipment/Supplies/Services**

- For data accrual, the study will not require additional equipment, supplies, or services that are not already typically rendered in the care of a preterm neonate. Both CHRISTUS and BAMC use SYSMEX XN2000 to run laboratory tests that will be pertinent to this study. Therefore, no additional equipment, supply, or service will be required that is not already part of standard of care of a premature neonate.
- For data collection and management, our study requires the use of REDCap, which will be provided by CHRISTUS.

### **Data Collection**

- The electronic medical records of CHRISTUS and Brooke Army Medical Center (BAMC) will be queried for patients who meet inclusion criteria as described above and consented for participation in the trial. Patient demographic information will be collected, along with other variables as outlined below:
  - Maternal Information
    - Age
    - Race / ethnicity: non-Hispanic White, non-Hispanic Black, Hispanic, Asian/Pacific Islander, Native
    - For patients at BAMC:
      - Mother Active Duty, Non-Active Duty, Retired
      - Rank of Active Duty: Enlisted versus Officer
    - Past medical history such as anemia, diabetes, mood disorder, hypertension, and more
    - Prenatal laboratory history: result of hepatitis B, syphilis, HIV, GBS status, blood type, rubella and varicella immunity status, gonorrhea and chlamydia status
    - Medication history to include use of antidepressants, anticonvulsants, insulin, aspirin, iron supplementation
    - Complications during delivery such as postpartum hemorrhage (>500 mL vaginal delivery, >1000mL c-section), magnesium around labor/delivery time-period, required pRBC transfusion
    - Blood type, antibody status

- Hemoglobin, hematocrit results prior to delivery
- Neonatal Information
  - Gestational age at birth
  - Birth order (first born, not first born)
  - Weight at birth
  - Delivery method: vaginal versus cesarean section
  - Instrumentation at delivery: vacuum assisted, forceps assisted, none
  - Race / ethnicity: non-Hispanic White, non-Hispanic Black, Hispanic, Other, Asian/Pacific Islander, Native
  - Phototherapy requirement
  - Blood type, DAT status
  - Delayed cord clamping
  - Hemoglobin, hematocrit, mean corpuscular volume at:
    - T0= first lab draw following starting iron
    - T1 = 2 weeks following T0
    - T#= every 2 week intervals until 36 weeks PMA or discharge
  - reticulocyte count, reticulocyte hemoglobin at:
    - T0= first lab draw following starting iron
    - T1 = 2 weeks following T0
    - T#= every 2 week intervals until 36 weeks PMA or discharge
  - Change in hematocrit, hemoglobin, retic count, retic hemoglobin between end of trial and T0
  - Ferritin, Serum TIBC, and iron levels at 36 weeks PMA
  - Darbepoetin / EPO use
  - Number of pRBC transfusions
  - Neonatal morbidities documented in the EMR which includes include anemia defined by unit guidelines based on the neonate's clinical status and corrected gestational age, necrotizing enterocolitis, sepsis, chronic lung disease, intubation, death, feeding difficulties
  - Neonatal severity scoring (NSOFA) at start of trial (T0) and every 2 weeks thereafter (T#)
  - Type of feed and calories from T0 to T#
  - Feeding volume at T0 to T#
  - Weekly growth parameters T0 to T# (weight, length, and head circumference)
  - Type of respiratory support T0 to T#
  - Blood draw volume T0 to T#
  - Transfusions from T0 to T#
  - Presence of specific diagnosis: constipation, feeding intolerance, infectious screen, clinical sepsis
- Data collected will include MRN; however, this will not be used in the analysis. All data will be deidentified before they are entered into REDCap for effective safeguard of information. Personnel

identified in this protocol will be responsible for collecting the data and will be the only persons who will have access to the de-identified data inputted on REDCap for further management and analysis.

## Data Analysis

- A sample size determination was conducted using Riskcalc.org (Chow S-C, Shao J, Wang H, Lokhnygina Y. Sample Size Calculations in Clinical Research. Third ed: Chapman and Hall/CRC; 2017.) and confirmed by [name] (BAMC Statistician). Sample size estimates are for type 1 error of 5% ( $\alpha = 0.05$ ), power ( $1-\beta$ ) of 80%, ratio of 1:1 of intervention to control. The effect size is determined by estimating the proportion of infants with Ret-Hgb >29 pg to be similar at 80% between daily versus EOD iron, with a margin of 20%. It was determined that a sample size of 100 patients would be needed for this study (50 for intervention, and 50 for control).
- A statistician who is blinded to the study allocation will analyze the data. All statistical analyses will be performed with IBM SPSS Statistics (Armonk, NY: IBM Corp) and JASP Team (2022). JASP, Version 0.16.1 (Netherlands: JASP Team). Descriptive statistics will be performed for all variables. Categorical data will be reported as percentages, and continuous data will be reported as medians with interquartile range or means with standard deviation. The two groups will be compared according to the intention to treat with the use of Student's t-tests, Mann-Whitney-U tests, chi-square analysis based on the outcome being evaluated. All p-values will be one-sided, with a statistical significance level of <0.05. Covariates to include gestational age, in-born versus out-born infants, ESA use, receipt of pRBC transfusion will be controlled for using a logistic regression model and will be reported with an odds ratio (OR) and 95% confidence intervals (CI). A medical monitor who is not involved in the study will be assigned prior to the initial enrollment of the trial to monitor the data periodically (every 3 months) to ensure the safety of the participants and the scientific integrity of the study. An interim analysis will be performed at halfway to target enrollment.

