## Objectives

- Primary objective: determine if daily versus EOD oral iron at the same dose per kilogram per day will achieve similar incidence of iron replete status at 36 weeks PMA.
- Secondary objective:
  - Characterize Ret-Hb levels in preterm infants
  - Identify the number of blood transfusions received between enrollment and 36 weeks' PMA between two groups
  - Determine prevalence of bronchopulmonary dysplasia between two groups
  - Identify the number with sepsis (defined as a positive blood or cerebrospinal fluid culture that was treated with antibiotics for at least 7 days) between two groups
  - Identify the number with necrotizing enterocolitis (NEC)/gastrointestinal perforation (medical NEC defined as  $\geq$ stage II Bell's criteria between two groups
  - Characterize growth (assessed by length gain at 36 weeks' PMA or at discharge if discharged before 36 weeks) between two groups

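### The 80% power holds only if 50 infants per arm have a 36-week Ret-Hb, but the protocol uses 100 as the number enrolled and makes no allowance for missing values

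*Protocol*

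**What the plan says.** The Study design section describes the trial this way: "This is a non-inferiority, blinded, randomized control trial". The primary objective is to find whether the two schedules "will achieve similar incidence of iron replete status at 36 weeks PMA", so the outcome is tied to one time point.

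The Data Analysis section takes 80% of infants as replete in both arms, a margin of 20 points, 80% power, 1:1 allocation and a type 1 error of 5%. It adds: "All p-values will be one-sided, with a statistical significance level of <0.05". From these inputs it concludes that "a sample size of 100 patients would be needed for this study (50 for intervention, and 50 for control"). It mentions no allowance for infants without an outcome.

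Three other statements bear on who will have that outcome:

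- Duration of Study continues accrual "until we have our target number of patients that meet inclusion criteria".
- Data Collection schedules Ret-Hb at "every 2 week intervals until 36 weeks PMA or discharge".
- Objectives has growth assessed at 36 weeks "or at discharge if discharged before 36 weeks". The primary outcome has no matching clause.

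Death is among the neonatal morbidities to be collected.

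**The concern.** A sample size formula for two proportions counts infants whose outcome is observed. The protocol takes the number from that formula and uses it as the point at which enrolment stops. Meeting the inclusion criteria is a status at entry; it does not mean that a 36-week value will exist.

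The two counts agree only if essentially every enrolled infant reaches the 36-week measurement. The protocol's own provisions allow for infants who do not: sampling may end at discharge, discharge may come before 36 weeks, and death is recorded. Infants born as late as 32 6/7 weeks are eligible, so early discharge cannot be dismissed as a case the design excludes.

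What is at stake is the accuracy of a stated operating characteristic. The 80% is given without conditions, although it depends on complete primary data. Lower power makes it less likely that the trial can show non-inferiority when the schedules truly perform alike. Loss of power does not by itself raise the chance of wrongly declaring non-inferiority.

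**Working it through.** **Inputs, all from the protocol's Data Analysis section.** Proportion replete 0.80 in each arm (true difference 0); margin 0.20; one-sided alpha 0.05 (z = 1.645); power 0.80 (z = 0.842); equal arms.

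**Step 1: reproduce the stated figure.** With unpooled variance, the number per arm is

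n = 2 × p(1 − p) × (z for alpha + z for power)² / margin²

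= 2 × 0.16 × (1.645 + 0.842)² / 0.20² = 49.46.

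Rounded up, this is 50 per arm and 100 in total, as the protocol states. The match shows that no attrition allowance is contained in the 100. The only slack is the rounding, 50 − 49.46 = 0.54 of an infant per arm.

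**Step 2: power as a function of evaluable infants.** By the same formula,

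power = Φ(0.20 / √(0.32 / n) − 1.645), with n the number per arm who have the primary measurement.

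- n = 50: √(0.32/50) = 0.0800; 0.20/0.0800 = 2.500; Φ(0.855) = 80.4%.
- n = 49: √(0.32/49) = 0.0808; 0.20/0.0808 = 2.475; Φ(0.830) = 79.7%.

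On the planning formula, power is thus just under 80% once one infant per arm is missing. Exact binomial enumeration of the corresponding unpooled z-test gives 80.0% at 49 per arm, so in practice the loss begins to matter beyond about one infant per arm.

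**Step 3: 100 enrolled, with some lacking a 36-week value.** The protocol gives no loss rate. The rates below are assumptions, taken as equal in the two arms.

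| Assumed loss | Evaluable per arm | Power, planning formula | Power, exact enumeration |
|---|---|---|---|
| 0% | 50 | 80.4% | 81.3% |
| 5% | 47.5 | 78.6% | not computed (n not whole) |
| 10% | 45 | 76.6% | 76.8% |
| 15% | 42.5 | 74.5% | not computed (n not whole) |
| 20% | 40 | 72.3% | 72.8% |

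Against 80.4% with no loss, the drop is 80.4 − 78.6 = 1.8 points at 5% loss and 80.4 − 72.3 = 8.1 points at 20%.

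**Step 4: does anything in the protocol supply the missing values?** The growth outcome takes the discharge value when discharge comes first. The primary outcome is given at 36 weeks only, in both the research question and the primary objective. The protocol does not say that a discharge Ret-Hb counts, and it does not provide for sampling after discharge. As written, nothing closes the gap.

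**The case against.** **Nothing is miscalculated.** This is correct. The 100 follows from its inputs, and a reader should not infer an arithmetic error. The fault lies in using an evaluable number as an enrolment number while stating the power without conditions.

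**The shortfall is possible, not certain.** This also stands. A reader might infer that the protocol expects early discharge, that fewer than 50 per arm will have the measurement, or that the loss will be 10% to 20%. The documents support none of these. The discharge clauses are conditional, the clause in Objectives concerns length gain and not Ret-Hb, death is only an item to be recorded, and no rate appears anywhere. What they do support is that there is no reserve and that power falls if values are missing.

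**The rule may be in the SAP.** Handling of missing outcomes often is, and its absence here is not the complaint. But this protocol itself fixes the sample size, the power and the accrual stop, and those statements need to agree. Intention to treat, which the Data Analysis section names, keeps infants in their randomised group; it does not create a 36-week value. Serial sampling up to discharge means that a late value may exist, so a rule counting it would shrink the shortfall. The protocol does not state such a rule.

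**Other assumptions matter as much.** This is true. By the same formula with 50 per arm, power is 87.6% if 85% are replete in both arms and 74.7% if 75% are. That puts the effect in proportion, but it does not make the unconditional 80% correct.

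**An inconclusive result would be misread as evidence against the every-other-day schedule.** A reader might infer this consequence. It is a guess about future readers, the documents say nothing on it, and it forms no part of the point.

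**Conclusion.** The point holds in a limited form. The sample size is correctly computed for 50 evaluable infants per arm, but the protocol applies it to enrolled infants. The stated power is therefore conditional on essentially complete 36-week data, a condition that the protocol does not state and that its own discharge provisions make uncertain.

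The effect is modest. The range of roughly 2 to 8 points rests on assumed losses of 5% to 20%, equal in both arms, with 80% replete in each arm, a 20-point margin and one-sided alpha 0.05. The direction is firm as long as infants without a 36-week value do not contribute to the primary analysis; the size cannot be settled from the documents.

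**What to change.** In the Data Analysis section, state that 50 per arm is the number with a 36-week Ret-Hb and that 80% power depends on reaching it. Beside it, give the power with 100 enrolled over a range of loss, explicitly labelled as an assumption: 80.4%, 78.6%, 76.6%, 74.5% and 72.3% at 0%, 5%, 10%, 15% and 20%. The sponsor should supply its own rates of discharge and of death before 36 weeks at the two sites, so that the relevant part of the range can be identified. No figure in the range should be written in as the expected loss before then.

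Alternatively, state that the last Ret-Hb before discharge counts as the primary outcome for infants discharged before 36 weeks, in line with the existing rule for growth. This would reduce the shortfall but not remove it, because infants who die would still need a rule. The power statement should then be reworded to match.

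The cost is a sentence or two and a less favourable power statement. No added enrolment is required.
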